6.1.6.1.4 Concomitant Medication

Missing concomitant medication dates will be handled in a similar fashion as described for AEs in [Section 6.1.6.1.3](#).

6.1.7 Pooling of Sites

As there are expected to be relatively few patients per site, the site will not be taken into account in the analyses. Therefore the question of pooling of sites does not arise.

6.1.8 Derived Variables

For derivations of the efficacy variables, see [Section 8](#). The following additional derived and computed variables have been initially identified as important for the analyses to be performed for this trial.

In case additional derived variables may be required: the SAP will not be amended for additional variables that are not related to the primary or secondary endpoints. Any additional derived or computed variables will be identified and documented in the SAS programs that create the analysis files. If the SAP is not amended, further derivations related to the primary and secondary endpoints will be described in the CSR.

6.1.8.1 Adverse events

Any adverse events occurring between last dose of RCT and OLE visit 1 will not be considered Treatment Emergent Adverse events (Aes occurring during study break). All other adverse events will be considered as treatment-emergent adverse events.

A TEAE will be considered treatment-related if the plausibility relationship to IMP is recorded on the eCRF as 'yes'. If the data on plausibility relationship to IMP is missing then the TEAE will be considered treatment-related.

A TEAE will be considered leading to permanent discontinuation of IMP (leading to withdrawal) if the action taken with IMP is recorded on the eCRF as 'trial medication stopped' or the outcome is recorded on the eCRF as 'patient died'.

A treatment-related TEAEs leading to withdrawal is a TEAE leading to permanent IMP discontinuation and considered treatment-related as per above definition.

A TEAE will be considered leading to IMP temporary discontinuation if the action taken with IMP is recorded on the eCRF as 'trial medication interrupted'.

A TEAE will be considered leading to permanent IMP dose reduction excluding permanent discontinuation if the action taken with IMP is recorded on the eCRF as 'dose reduced'.

A TEAE will be considered fatal if the outcome is recorded on the eCRF as 'patient died'.

The time to first onset of AE will be calculated for TEAEs as:

$$\text{Start date of AE} - \text{Day 1} + 1$$

The time to AE resolution will be calculated for TEAEs as:

$$\text{Stop date of AE} - \text{Start date of AE} + 1$$

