PRN	Packaging reference number
PsS	Standardized Psychosocial Summary

Study Code: GWND19002
 EudraCT Number: 2019-001605-24
 Clinical Protocol V2 18Dec19

Abbreviation or special term	Definition or Explanation
PVD	Pharmacovigilance Department
QoL	Quality of life
RCT	Randomized controlled trial
RSBQ	Rett Syndrome Behaviour Questionnaire
RTSM	Randomization and Trial Supply Management
RTT	Rett syndrome
SAE	Serious adverse event
SAP	Statistical analysis plan
SF-36	36-item Short Form
SUSAR	Suspected unexpected serious adverse reaction
TBL	Total bilirubin
TEAE	Treatment-emergent adverse event
THC	Δ^9 -tetrahydrocannabinol
UGT	Uridine 5'-diphospho-glucuronosyltransferase
ULN	Upper limit of normal
US	United States

Study Code: GWND19002
 EudraCT Number: 2019-001605-24
 Clinical Protocol V2 18Dec19

Definition of Terms

Term	Definition
Caregiver	An assigned patient's parent or designated care provider.
Day 1	The day a patient first receives the investigational medicinal product in this trial.
End of treatment	Completion of the treatment period (Visit 14 [Day 729]), or withdrawal.
End of trial	Last patient's last visit/telephone call.
Enrolled patient	Any patient whose parent(s)/legal representative has provided written informed consent for the patient to take part in the trial and, if possessing adequate understanding to do so, who has provided informed assent.
International normalized ratio	A calculation made to standardize prothrombin time.
Investigational medicinal product	The term used to describe both investigational active product and reference therapy (placebo).
Investigator	Trial principal investigator or a formally delegated study physician.
Methyl-CpG-binding protein 2	Methyl-CpG-binding protein 2 is denoted differently in this document: the italicized abbreviation MECP2 denotes the human gene, the italicized Mecp2 denotes the mouse gene, and the nonitalicized abbreviation MeCP2 denotes the protein.
Postregression	≥ 6 months since the last loss of hand use or verbal language or gross motor regression.

Study Code: GWND19002
EudraCT Number: 2019-001605-24
Clinical Protocol V2 18Dec19

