4 EXPERIMENTAL PLAN

4.1 Trial Design

This is a multicenter, OLE trial for patients with RTT who have completed the randomized, double blind, placebo-controlled trial (GWND18064).

Entry to this OLE trial is recommended to be on the same day as Visit 9 of the randomized controlled trial (RCT), GWND18064; however, patients may enter the OLE up to the RCT follow-up visit (Visit 11).

All patients entering this OLE trial will begin dosing with 5 mg/kg/day GWP42003-P (2.5 mg/kg b.i.d.) on Day 1. Patients will be observed, and after 1 week, the dose may further be escalated, at the investigator's discretion, up to 15 mg/kg/day GWP42003-P (7.5 mg/kg b.i.d.) in weekly increments of 5 mg/kg/day (2.5 mg/kg b.i.d.).

Patients should then remain on a stable dose of GWP42003-P for the duration of the maintenance period of the trial (up to 104 weeks), with the option for doses to be decreased or increased to a maximum dose of 20 mg/kg/day (10 mg/kg b.i.d.) based on clinical response and tolerability, as deemed necessary by the investigator, until the optimal dose is found. Patients whose dose has been decreased can have their dose increased again if tolerability improves.

At the end of treatment (Visit 14 [Day 729]), the dose of GWP42003-P will be reduced over a 10-day taper period, and patients will enter the 4-week follow-up period.

If a patient permanently discontinues treatment at any point during the trial, GWP42003-P should be gradually reduced over 10 days (unless inadvisable due to an AE). The patient should attend a withdrawal visit (Visit 14) as soon as possible after the decision is made to permanently discontinue GWP42003-P. If applicable, the patient will taper GWP42003-P, attend the End of Taper visit (Visit 15), and then complete the 4-week follow-up period.

A schematic ([Figure 1-1](#)), presented at the end of [Section 1](#), depicts the overall trial design. More detailed information on treatment and trial procedures is provided in [Section 8](#) and [Section 9](#), respectively.

Study Code: GWND19002
EudraCT Number: 2019-001605-24
Clinical Protocol V2 18Dec19

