9.2.15 Adverse Events

All AEs (including SAEs) occurring during the trial will be reported on the running logs in the AE section of the eCRF. This includes all events from the time following screening (Visit 1) up to and including the post-trial follow-up visit (Visit 16), whether or not attributed to GWP42003-P and observed by the investigator or patient.

* For the patient's expected seizure types, these do not routinely require documentation as AEs. However, any worsening, including a change in the pattern or severity of seizures should be documented in the eCRF if deemed to meet the definition of an AE, in the investigator's opinion.

Study Code: GWND19002
EudraCT Number: 2019-001605-24
Clinical Protocol V2 18Dec19

Any AE that meets SAE criteria should still be reported as a SAE.

Serious adverse events must be reported to GW Pharmacovigilance Department (PVD) within 24 hours of discovery or notification of the event via recording in the eCRF.

Refer to [Section 12](#) for definitions, procedures, and further information on AE reporting.

Study Code: GWND19002
 EudraCT Number: 2019-001605-24
 Clinical Protocol V2 18Dec19

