13.6.2.2 Adverse Events

AEs will be coded according to the Medical Dictionary for Regulatory Activities dictionary.

A treatment-emergent adverse event (TEAE) is one that started or worsened in severity or seriousness following the first dose of IMP.

Descriptive presentations of TEAEs will be given by preferred term and system organ class. The number of patients reporting at least 1 TEAE will be provided.

The following summaries will be produced as a minimum:

- All-causality TEAEs.
- Treatment-related AEs.
- All-causality TEAEs by maximal severity.
- All-causality serious TEAEs.
- Treatment-related serious TEAEs.
- TEAEs reported as leading to permanent cessation of IMP.
- Fatal TEAEs.

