6.1.6.1.3 Adverse Events

Missing and/or incomplete dates for AEs will be imputed in a manner resulting in the earliest onset or the longest duration during the treatment period, while ensuring that the start date is not after the stop date, i.e. missing start dates will be imputed as the first day of the month/first month of the year and missing stop dates will be imputed as the last day of the month/last day of the year, while ensuring that the start date is not after the stop date. Upper and lower limits of imputation will be date of Visit 1 and last visit date as defined in [section 6.1.3](#), and events occurring on date of Visit 1 will be assumed post-IMP. Stop dates will not be imputed if the AE is ongoing.

Imputed dates will be used for calculation of time to first onset and time to AE resolution, they will not be presented in AE listings.

A worst-case approach will be followed in the event of missing severity or causality data. If the

severity is missing, 'Severe' will be imputed. If causality data is missing for a treatment emergent AE (TEAE), 'Yes' will be imputed for the question 'Plausible relationship to study medication'.

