9.1 Adverse Events

All reported AEs will be classified by system organ class (SOC), and preferred term (PT) and lower level term using Version 21.1 of MedDRA or higher.

The following summaries will be generated (counts are by patient unless specified otherwise):

Overall summary of TEAEs, including following description:

- Summary of TEAEs.
- Summary of treatment-related TEAEs.
- Summary of TEAEs leading to permanent discontinuation of IMP.
- Summary of serious TEAEs.
- Summary of treatment-related serious TEAEs.

Following summaries will be presented by SOC and PT:

- Summary of TEAEs
- Summary of treatment-related TEAEs
- Summary of TEAEs by maximal severity.
- Summary of serious TEAEs
- Summary of non-serious TEAEs.
- Summary of treatment-related serious TEAEs.
- Summary of TEAEs leading to permanent discontinuation of IMP.
- Summary of treatment-related TEAEs leading to permanent discontinuation of IMP.

- Summary of TEAEs leading to IMP dose reduction excluding permanent discontinuation (by resolution and overall).
- Summary of treatment-related TEAEs leading to IMP dose reduction excluding permanent discontinuation (by resolution and overall).
- Summary of TEAEs leading to IMP interrupted (by resolution and overall).
- Summary of treatment-related TEAEs leading to IMP interrupted (by resolution and overall).
- Summary of fatal TEAEs.
- Summary of TEAEs by time of first onset of AE.
- Summary of TEAEs by time to AE resolution.
- Summary of TEAEs reported in $\geq 2\%$ of patients (after rounding)
- List of patients experiencing TEAEs by SOC and preferred term.

For the summary of TEAEs by maximal severity, for each patient, the worst severity recorded by PT, SOC and overall will be used for summary purposes. If severity is missing, the worst case (severe) will be assumed.

For summaries by resolution, AEs with an outcome of ‘recovered’ or ‘recovered with sequelae’ will be summarized as ‘Resolved’ and AEs with an outcome of ‘continuing’, ‘patient died’ or those with a missing outcome will be summarized as ‘Not resolved’.

For the summary of TEAEs by time of first onset of AE, data will be summarized under the following categories:

- Month 1 (Day 1–29).
- Month 2 (Day 30–59).
- Month 3 (Day 60–89).
- Month 4-6 (Day 90–179).
- Month 7-9 (Day 180–269).
- Month 10-12 (Day 270–359).
- >1 year (> Day 359).

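### SAP 6.1.8.1 defines treatment-emergent AEs by exclusion only, so any event in the data that began during RCT dosing would count as an OLE TEAE

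*SAP*

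**What the plan says.** SAP 6.1.8.1 makes a single exclusion: "Any adverse events occurring between last dose of RCT and OLE visit 1 will not be considered Treatment Emergent Adverse events". The next sentence is the default: "All other adverse events will be considered as treatment-emergent adverse events". Neither sentence refers to onset or worsening after a dose.

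Protocol V2 13.6.2.2 uses a different rule: "A treatment-emergent adverse event (TEAE) is one that started or worsened in severity or seriousness following the first dose of IMP". It does not say which trial's first dose is meant, and the protocol's Definition of Terms makes IMP cover placebo as well as active product.

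Other text bears on which events are in scope:

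- Protocol V2 9.2.15, on what goes into the AE log: "This includes all events from the time following screening (Visit 1) up to and including the post-trial follow-up visit (Visit 16".
- SAP 6.1.6.1.3, on missing or partial AE dates: "Upper and lower limits of imputation will be date of Visit 1 and last visit date".
- SAP 6.1.8.1 calculates time to first onset as start date minus Day 1 plus 1, and SAP 9.1 bins it in categories of which the earliest begins at Day 1.
- SAP 9.5, which sets out how the analyses differ from the protocol, mentions the added OLE baseline but no new TEAE definition.

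**The concern.** Safety is the primary endpoint of this trial, AEs head the list of safety measures, and almost every AE table in SAP 9.1 is a table of TEAEs. A definition by exclusion lets in whatever is not named. Events that began on RCT treatment are not named.

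The one filter also does least in the intended pathway. Protocol 4.1 says: "Entry to this OLE trial is recommended to be on the same day as Visit 9 of the randomized controlled trial (RCT". With same-day entry the break has roughly zero length, so the exclusion removes almost nothing.

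At stake is attribution. An event that began on RCT placebo would be reported as emerging on open-label GWP42003-P. It would sit in the former-placebo columns of SAP Table 2 next to events that did begin on active drug.

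**Working it through.** The plan has no figure to reproduce: there is no sample size calculation and no hypothesis test. The check applies each rule to every possible start date.

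| AE start date | SAP 6.1.8.1 as written | Onset or worsening from first OLE dose | Onset day (start − Day 1 + 1) |
|---|---|---|---|
| Before or during RCT dosing | TEAE | TEAE only if it worsens in the OLE | 0 or less |
| After last RCT dose, before OLE Visit 1 | Not a TEAE | TEAE only if it worsens in the OLE | 0 or less |
| OLE Visit 1 onward | TEAE | TEAE | 1 or more |

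The rules part in the first row. (Protocol 12.5 asks for a new record when a pretreatment event worsens in severity after the first dose, so a real worsening should arrive with its own later start date.)

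**Worked date (assumed).** An AE starts 40 days before OLE Visit 1, on RCT placebo, and the last RCT dose is on the day of Visit 1. It is outside the break, so it is a TEAE. Its onset day is −40 + 1 = −39. The first category in SAP 9.1 covers Days 1–29, so the event is in the overall TEAE table and in no row of the onset table.

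**Knock-on effects within the SAP.**

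- The onset table counts only a patient's first occurrence of an AE. If the same AE occurs in the RCT and again in the OLE, the RCT onset is the first, and the OLE onset drops out of every category.
- SAP 6.1.8.4 counts dosing days from OLE Day 1. RCT-period events would be set against OLE-only exposure.
- The Visit 1 limit in SAP 6.1.6.1.3 applies only to imputed dates. A fully dated event has no such limit.

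**How such a record could arise.** An AE review is required for all patients at OLE Visit 1 (Protocol V2 9.1.1.1). An event that began on RCT treatment and is still ongoing could be logged there with its true start date. SAP 6.1.4 also provides for day numbers before Day 1.

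**Size.** None of the rates below is in the documents. Let p be the true proportion of patients with an OLE TEAE and r the proportion with an RCT-period AE in the data, independent of p. The reported proportion is 1 − (1 − p)(1 − r). Take p = 0.5.

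- No RCT-onset records (r = 0): 1 − 0.5 × 1 = 0.50, no effect.
- Only ongoing events carried over, in a proportion c: 0.5 + 0.5c, a rise of half of c.
- Full RCT log merged: r = 0.3 gives 1 − 0.5 × 0.7 = 0.65; r = 0.5 gives 1 − 0.5 × 0.5 = 0.75; r = 0.7 gives 1 − 0.5 × 0.3 = 0.85.
- Full merge with the greatest overlap within patients: max(0.5, r), which is 0.50 to 0.70 for r from 0.3 to 0.7.

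**The case against.** The best defence is that the AE set contains OLE events only. The log runs from OLE Visit 1 to Visit 16, the SAP covers this trial's reporting, date imputation is bounded by Visit 1, the onset categories start at Day 1, and SAP 7.3.2 limits medical history to what the lead-in study had not already recorded. On that reading, the default sentence means all other events in the OLE log. Same-day entry then leaves nothing to exclude, and the lack of a category before Day 1 shows that such events were not expected.

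Much of this stands. A reader might infer that, because the SAP bothers to exclude break events, the RCT AE database must be pooled. The documents do not support that. Break events have their own route in, through the Visit 1 AE review, and the annex allows entry after the RCT follow-up visit, so there can be an interval that the RCT never covered. No text says that RCT AE records are merged.

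Nor does the protocol clearly require onset after the first OLE dose: it leaves open whose first dose counts. It also lists AEs among the measures assessed against the RCT prerandomization baseline (Protocol 4.1.1, repeated in SAP 2.2.2), which could be read as cumulative reporting.

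Two further mitigations are fair. The trial is descriptive, and the TEAE listing shows start day relative to Day 1, so an early onset would be visible to someone who looked. On the other side, SAP 4.2.2 plans no data review meeting.

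What the defence does not supply is a filter. None of the provisions it relies on is written as a condition on fully dated events in the TEAE rule.

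**Conclusion.** The rule is wrong as written. It omits the onset-or-worsening condition of Protocol 13.6.2.2, does not declare the change, and does not fit the SAP's own Day 1 framework. Any event in the data with onset during RCT dosing would be misclassified in the primary safety tables.

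How much this matters depends on a fact that the documents leave open. The effect is zero with no such records, small if only ongoing events carry over to few patients who have no OLE event, and large only with a full merge. A reader might take 65–85% as the incidence to expect. It is not: it rests on an assumed 50% true incidence, an assumed 30–70% RCT incidence, independence, and a complete merge. Positive correlation within patients lowers it, to 50–70% at greatest overlap.

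Rating: should-fix, with moderate confidence.

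**What to change.** State first whether RCT AE records are part of the OLE analysis data, and whether OLE-only or cumulative reporting is intended.

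For OLE-only reporting, replace the two sentences in SAP 6.1.8.1 with: a TEAE is an AE with onset, or worsening in severity or seriousness, on or after the first OLE dose (Day 1) and up to Visit 16; AEs with earlier onset, whether on RCT treatment or in the break, are listed separately and not counted. This keeps the protocol's criterion, names the dose, and agrees with the existing onset formula and categories. It costs one SAP passage and one programming condition.

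If cumulative RCT plus OLE reporting is intended, say so, and tabulate RCT-period events separately, above all those on placebo. The onset categories and exposure days would then need RCT counterparts, which is more work.

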9.1.2 Dipstick urinalysis (provided urine can be obtained)Telephone Visits

9.1.2.1 Visits 2 (Day 8 [± 3]) and 3 (Day 15 [± 3])

A visit window of ± 3 days from the scheduled visit date is permitted, but it is preferred that the visit is performed on the scheduled visit day, where possible.

Telephone visits will be conducted by a center nurse (the center investigator only needs to be involved if necessary, e.g., if any concerns are raised during the call). Information regarding changes to concomitant medications and AEs will be reviewed. The center (the nurse and, if necessary, the investigator) must assess adherence to the dosing schedule.

Study Code: GWND19002
EudraCT Number: 2019-001605-24
Clinical Protocol V2 18Dec19

9.1.2.2 Visit 16 (28 days after last dose IMP [+ 7], Follow-up, End of Trial)

A visit window of + 7 days from the scheduled visit date is permitted, but it is preferred that the visit is performed on the scheduled visit day, where possible. This visit marks the end of the trial.

Visit 16 constitutes the last scheduled safety follow-up. The purpose of the visit is to ascertain the status of AEs continuing after the cessation of GWP42003-P or any new AEs commencing after discontinuation. All causally related AEs that result in a patient's early termination from the trial or are present at the end of the trial should be followed up until a satisfactory resolution occurs, i.e., until the AE resolves or is considered clinically insignificant, or until the investigator is satisfied that the AE is not related to GWP42003-P and needs no further investigation. Information regarding changes to concomitant medications will be reviewed.

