12.3 Reporting Procedures for Serious Adverse Events

All SAEs occurring during the trial must be reported to GW with any other supporting information and recorded in the AE section of the eCRF. Any ongoing SAEs should be followed up until resolution, wherever possible. For all deaths, the working diagnosis or cause of death as stated on a death certificate, available autopsy reports, and relevant medical reports should be sent to GW promptly.

All SAEs must be recorded in the eCRF within 24 hours of discovery or notification of the event. GW Research Ltd PVD will be automatically notified that an SAE has been recorded. Any additional information required for a case (follow-up or corrections to the original case) will be requested by GW PVD through eCRF queries.

The investigator should continue to document all AEs that occur up to the last formal safety follow-up (Visit 16). If the investigator subsequently becomes aware of any deaths or a new GWP42003-P-related SAE after the last formal follow-up period of the trial, these should still be reported to GW PVD.

Any other problem discovered after Visit 10 that is deemed to be an unexpected safety issue and is likely to have an impact on patients who have taken part in the trial must be

Study Code: GWND19002
EudraCT Number: 2019-001605-24
Clinical Protocol V2 18Dec19

treated as an SAE and reported to GW PVD. Such post-trial SAEs do not need to be recorded on the patient's eCRF if editing rights to the eCRF have been removed due to the final trial data lock. GW Research Ltd PVD may request safety follow-up information after the final trial visit in order to investigate a potential safety issue.

Contact details for GW PVD are provided at the front of the center files for all trial centers.

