12.6 Reporting Procedures for All Adverse Events

All AEs (including SAEs) occurring during the trial will be reported on the running logs in the AE section of the eCRF. This includes all events from the time following screening (Visit 1) up to and including the post-trial safety follow-up visit (Visit 16), whether or not attributed to GWP42003-P and observed by the investigator or patient.

For the patient's expected seizure types, these do not routinely require documentation as AEs. However, any worsening, including a change in the pattern or severity of seizures, should be documented in the CRF if deemed to meet the definition of an AE, in the investigator's opinion.

Any AE that meets the SAE criteria should still be reported as an SAE.

The following information will need to be provided for all AEs:

A) Adverse Event (Diagnosis or Syndrome, if Known, or Signs and Symptoms)

Where the investigator cannot determine a diagnosis, signs or symptoms should be recorded in the AE section of the eCRF. Once a diagnosis has been determined, the AE section of the eCRF must be updated to reflect the diagnosis in replacement of the original symptoms. In circumstances where only a provisional diagnosis is possible (working diagnosis), the eCRF must be updated to reflect the provisional diagnosis in replacement of the original symptoms. In some circumstances, it may be relevant for the investigator to include the symptoms alongside the diagnosis in the verbatim event

Study Code: GWND19002
EudraCT Number: 2019-001605-24
Clinical Protocol V2 18Dec19

description. However, the diagnosis (full or provisional) should be clearly stated, e.g., fever and malaise due to respiratory tract infection.

B) Adverse Event Start Date and Stop Date

The start and stop dates of the event must be provided. All AEs require these fields to be completed in full. Partial dates or missing dates are not normally acceptable, and significant effort must be undertaken to obtain any unknown information. If a precise date is not known, an estimated date should be provided instead. When a complete date cannot be given, record as much information as possible (i.e., the month and year or, in exceptional circumstances, just the year). When the actual start date becomes known, the eCRF must be updated to replace the previously recorded date.

C) Outcome

The outcome of the event must be recorded accurately and classified into one of the following categories:

- Recovered
- Recovered with sequelae

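### SAP 6.1.8.1 counts a fatal event that begins after dosing has ended as the reason for stopping drug, so adverse-event discontinuations can be overstated, probably by no more than one patient

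*SAP*

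**What the plan says.** The rule is in SAP 6.1.8.1 and opens "A TEAE will be considered leading to permanent discontinuation of IMP (leading to withdrawal"). Two conditions follow, and either is enough. One is that action taken with IMP shows the drug was stopped; the other is "or the outcome is recorded on the eCRF as" *patient died*. Nothing requires that the patient was still taking IMP when the fatal event began.

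The same section sets aside only events falling between the last RCT dose and OLE Visit 1. Of the rest it says: "All other adverse events will be considered as treatment-emergent adverse events". No upper limit is tied to the last OLE dose.

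Protocol V2 section 12.6 has adverse events recorded "up to and including the post-trial safety follow-up visit (Visit 16"). The heading of section 9.1.2.2 places that contact in time: "Visit 16 (28 days after last dose IMP [+ 7], Follow-up, End of Trial").

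The result is reported in SAP 9.1 as "Summary of TEAEs leading to permanent discontinuation of IMP", once as a line of the overall TEAE summary and again by SOC and PT. A treatment-related version by SOC and PT is also planned.

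**The concern.** An event cannot be the cause of a stop that came before it. Under the rule as written, a patient who finished treatment, or stopped for an administrative reason, and then had a fatal event during off-drug follow-up is classified as having discontinued because of that event. The disposition table in SAP 7.1 would show the same patient as a completer or under a different reason, so two planned outputs would disagree.

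Long-term safety is the primary objective, and this count is one of the five lines of the overall TEAE summary. The situation is also foreseeable: the SAP overview says the sponsor decided to discontinue both the lead-in trial and the extension, so stops unrelated to adverse events, each followed by a safety follow-up, are to be expected.

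**Working it through.** The plan gives no figure for this count, so there is nothing to reproduce. The check traces the rule and then gives a sense of scale.

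**Tracing one patient**

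1. The patient takes the last dose (end of taper) and disposition records completion.
2. A fatal event starts 10 days later. That is before Visit 16, so it is recorded (Protocol V2 12.6, 9.1.2.2).
3. It does not fall between the RCT and the OLE, so it is a TEAE (SAP 6.1.8.1).
4. Action taken may properly be recorded as none, because there was no drug left to stop. Protocol V2 12.6 collects action taken separately from outcome.
5. The outcome alone meets the second condition, so the event counts as leading to permanent discontinuation.
6. Counts are by patient (SAP 9.1). The total changes only if this patient has no other TEAE coded as stopping drug.
7. The treatment-related version changes only if causality is yes, or is missing and therefore taken as related (SAP 6.1.8.1).

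**How long the window is**

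Off-drug share of observation = F / (day of last dose + F), with F = 28 or 35 days.

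- Completer, last dose Day 739: 28/767 = 3.7%; 35/774 = 4.5%.
- Earlier stop, last dose assumed at Day 207: 28/235 = 11.9%; 35/242 = 14.5%.

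**How many patients**

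The documents give no mortality rate, so the rate r is an assumption, ranged from 0.5% to 5% per patient-year. With the planned N of 252 (Protocol V2 13.1), expected post-treatment deaths = 252 × F/365.25 × r, and P(at least one) = 1 − (1 − r × F/365.25)^252.

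| r per year | F (days) | Expected deaths | P(at least one) |
|---|---|---|---|
| 0.5% | 28 | 0.10 | 9% |
| 1% | 28 | 0.19 | 18% |
| 2% | 35 | 0.48 | 38% |
| 5% | 35 | 1.21 | 70% |

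These are generous figures. They assume that all 252 patients enrol and complete follow-up, that every such fatal event began after the last dose, and that none of these patients had another TEAE coded as stopping drug.

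**Effect of one such patient**

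100/N percentage points: 0.4 at N = 252. For assumed smaller groups it is 1.0 at 100, 2.0 at 50 and 4.0 at 25. SAP Table 2 divides results into four columns, so column denominators will be below the total. As a hypothetical example, 10 true adverse-event discontinuations plus one such death give 11/252 = 4.4% instead of 10/252 = 4.0%.

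**The case against.** The fatal limb has a proper purpose. The action-taken field has no category for death, so a fatal event on treatment could be coded as no action although dosing ended with it; the limb recovers that patient. It also fits the SAP's worst-case handling of missing severity and causality (SAP 6.1.6.1.3). Any error makes the drug look worse, not better. The planned outputs would let a careful reader find the case: a fatal TEAE table, listings with start and stop days, and disposition by reason. The trial is descriptive, so no test or decision rule depends on the row. All of this stands. It supports keeping the limb and treating the matter as minor. It does not make the count correct, because a separate table of deaths leaves the discontinuation row unchanged.

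A reader might infer more than the documents support:

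- **That deaths after Visit 16 also enter.** Protocol V2 12.3 says "If the investigator subsequently becomes aware of any deaths" after the last follow-up, these still go to the sponsor's pharmacovigilance department. But routine collection ends at Visit 16, the same section says post-trial SAEs need not be entered once eCRF editing rights are withdrawn, and the SAP rule reads the eCRF. The documents do not show such deaths reaching this count.
- **That the SAP contradicts the protocol.** Protocol V2 13.6.2.2 asks for "TEAEs reported as leading to permanent cessation of IMP", but in a list described as a minimum, and section 13 leaves further detail to the SAP. Defining the term is such a detail.
- **That all fatal events are misclassified, or that all post-treatment deaths reach the treatment-related row.** Fatal events that themselves end dosing are rightly counted, and the treatment-related row also needs causality of yes or missing.

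**Conclusion.** The point holds, as a small definitional error. Applied exactly, SAP 6.1.8.1 labels a fatal event that begins in off-drug follow-up as the cause of a stop that had already taken place. The total is affected only when the patient had completed treatment or stopped for a non-AE reason, the fatal event was recorded by Visit 16, and no other TEAE was coded as stopping drug. The rule can add patients but never remove them.

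The likely number is 0 or 1. That rests on the assumed mortality range, and the SAP gives no final N for a trial that was stopped early. Fewer patients make such a case less likely, but each one then weighs more. A large or certain inflation of the discontinuation rate cannot be inferred from the documents.

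**What to change.** Add a condition to the fatal limb in SAP 6.1.8.1, along these lines:

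> A fatal outcome by itself counts as leading to permanent discontinuation only if the TEAE started on or before the date of last IMP dose (taper included) and the disposition form does not record that, before death, the patient had completed treatment or stopped IMP for another reason.

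The reference to the time before death settles the case of an event that starts on treatment in a patient who then completes as scheduled and dies later.

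Keep the limb for deaths on treatment, keep all deaths in the fatal TEAE table, and reconcile the discontinuation count with the disposition table before the report is final.

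The cost is one clause and a small programming change. No new data are needed: AE start dates and disposition reasons are collected, and SAP 7.4 has the final dose date recorded for both the treatment period and the taper.
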